Primary Objectives and Primary Endpoint	
Primary objective: To evaluate the potential efficacy of deferoxamine in reducing the risk of postoperative AKI in patients undergoing cardiac surgery.
 
Primary endpoint: Incidence of postoperative AKI, defined as follows: urine output <0.5 ml/kg/h for 6 consecutive hours (assessed within the first 48h or until the Foley catheter is removed, whichever occurs first); an increase in serum creatinine ≥0.3 mg/dl within the first 48h; an increase in serum creatinine ≥50% in the first 7 days; or receipt of renal replacement therapy in the first 7 days.

Secondary Objectives and Corresponding Endpoints	
Secondary objectives:
 
 ▪ To evaluate the potential efficacy of deferoxamine in reducing renal tubular injury in patients undergoing cardiac surgery. ▪ To evaluate the potential efficacy of deferoxamine in reducing the risk of postoperative myocardial injury, atrial fibrillation, prolonged mechanical ventilation, and sepsis in patients undergoing cardiac surgery. 
Secondary endpoints:
 
 ▪ Urinary markers of tubular injury, NGAL and KIM-1, assessed preoperatively, at the end of CPB, on arrival to the ICU, and daily for 2 days postoperatively. ▪ Postoperative myocardial injury, atrial fibrillation, prolonged mechanical ventilation, and sepsis within 7 days following cardiac surgery.
Exploratory Objectives and Corresponding Endpoints	
Exploratory objectives: To test the effects of deferoxamine on circulating markers of iron, oxidative stress, and inflammation
 
Exploratory endpoints: Circulating markers of iron status (catalytic iron, total iron, total iron binding capacity, ferritin, and hepcidin), oxidative stress (F[2]-isoprostane and myeloperoxidase), and inflammation (monocyte phenotype), each assessed pre- and postoperatively.

Sites	Brigham and Women's Hospital (BWH) Massachusetts General Hospital (MGH) Beth Israel Deaconess Medical Center (BIDMC)
Study Duration	Estimated total study duration is 4 years
Data and Safety Monitoring Committee (DSMB)	A DSMB will convene prior to study launch and after enrollment of 10, 25, 50, and 75% of the total enrollment has taken place to review safety data and any unanticipated problems. The DSMB will make recommendations as needed. The DSMB will not perform a futility analysis or consider early study completion for efficacy.

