1.2.2 Clinical studies

Clinical studies supporting the proposed research include the demonstration of elevated levels of catalytic iron in the circulation of patients at risk of AKI, including both cardiac surgery-associated AKI and AKI in the setting of critical illness.

Catalytic iron and cardiac surgery-associated AKI

We measured plasma catalytic iron pre-, intra-, and postoperatively in 250 adults undergoing cardiac surgery with CPB.²⁷ Catalytic iron levels peaked at the end of CPB, and were higher in patients who developed the composite endpoint of postoperative AKI requiring RRT or death (RRT/death) (Figure 1). In multivariable models, patients with catalytic iron levels in the highest versus lowest quartile on postoperative day 1 had a **3.99-fold higher odds of AKI** (95% CI, 1.60 to 9.93) and a **6.71-fold higher odds of RRT/death** (95% CI, 1.37 to 32.87). Finally, longer duration of CPB ($P<0.001$) and greater number of RBC transfusions ($P<0.01$) each associated with higher catalytic iron postoperatively, consistent with hemolysis as an important source of catalytic iron in this context.²⁷

Catalytic iron and critical illness-associated AKI

We measured plasma catalytic iron levels in 121 patients within 24h of arrival to the intensive care unit (ICU), and found that higher concentrations associated with a greater risk of AKI in both univariate and multivariable models (adjusted odds ratio per 1-SD higher catalytic iron, 1.67; 95% CI, 1.04 to 2.67).⁶⁵ We also measured plasma catalytic iron and other iron parameters in 807 patients with AKI requiring RRT who enrolled in the Acute renal failure Trial Network (ATN) study. Higher quintiles of catalytic iron associated with a monotonic increase in the risk of 60-day mortality (Figure 2A).⁶⁶ Other iron markers were also associated with death, but the magnitude of association was greatest for catalytic iron (Figure 2B).⁶⁶

Conclusions from these data

1. Catalytic iron levels are markedly elevated following CPB.
2. Catalytic iron levels are significantly higher among patients who develop AKI and RRT/death following CPB.
3. Catalytic iron levels rise acutely and early in the course of AKI following CPB surgery, a setting in which the timing of renal injury is known. This establishes CPB surgery as an important setting to test the efficacy of iron chelation in reducing the risk of AKI, as we now propose.

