The blood volumes shown in **Figure 4** represent the minimum volume required to perform the comprehensive assays for the study. Preoperatively and at the end of CPB we will collect 25mL of blood, which will allow us to isolate peripheral blood mononuclear cells (PBMCs) and store them in liquid nitrogen for immunophenotyping, including flow cytometry, RNA sequencing (RNA-Seq), and qPCR. Specifically, collection of 25mL of blood will be divided as 20mL of plasma and 5mL of serum. The 20mL of plasma will allow us to isolate approximately 20×10^6 PBMCs, since each mL of blood contains approximately 10^6 PBMCs. We will aliquot and store these 20×10^6 PBMCs into four aliquots of 5×10^6 PBMCs each. Aliquot #1 will be used for flow cytometry studies to assess monocyte expression of IL-6, TNF α , HLA-DR, TLR4, PD-L1, IL-1 β , IL-10, CD163, heme oxygenase-1, ferroportin, transferrin receptor 1, and iron uptake transporters (DMT1, ZIP14). These markers will be used to assess the effect of DFO (versus normal saline) on the inflammatory phenotype of monocytes postoperatively. Further, they will be used to assess whether the effect of DFO versus normal saline on clinical parameters (AKI and extrarenal acute organ injury) differs according to preoperative differences in monocyte expression of these markers. Aliquot #2 will be used to quantify intracellular iron concentrations using the calcein-AM method.⁸⁴ Aliquot #3 will be used for RNA-Seq of monocytes to facilitate discovery of novel transcripts influenced by DFO. Aliquot #4 will be used for qPCR to validate the targets identified by RNA-Seq.

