The volume of blood drawn at the other time points will be 10mL, as shown in **Figure 4**. This will include 5mL of blood drawn into a serum vacutainer and 5mL drawn into a heparinized plasma vacutainer. The serum and plasma will be centrifuged, subaliquoted, and stored at -80°C . 5mL of blood contains approximately 2.5mL of plasma/serum (approximately 50% of whole blood is plasma/serum), which will allow us to archive eight 300 μL plasma and serum aliquots at each time point. These aliquots will be used to measure the following parameters, and for storage for future hypotheses and mechanistic pathways: catalytic iron, total iron, total iron binding capacity, ferritin, hepcidin, troponin I, and oxidative stress parameters (F[2]-isoprostane and myeloperoxidase). Finally, we will collect the buffy coat (for DNA isolation) on ICU arrival and on post-operative day (POD) 1 (**Figure 4**).

Patients with a hemoglobin level <8 g/dl are excluded (section 3.2). Additionally, if during the course of the study the patient's clinical team determines that collection of blood is unsafe for the patient (e.g., if the patient is experiencing major bleeding postoperatively) then the blood sample will not be collected until the clinical team determines that it is safe. Urine will be collected for assessment of markers of tubular injury, including NGAL and KIM-1.

Sample processing, cataloging, storing, and monitoring

We will centrifuge samples as soon as possible and no more than 6h after collection and store the plasma, serum, and urine at -80C. At two time points (preoperatively and at the end of CPB) we will also isolate PBMCs and store them in liquid nitrogen. We will use screw cap micro tubes for plasma, serum, and urine samples, each pre-labeled with a unique barcode and a printed label. Each site will catalogue the date and time of collection, processing, and storage at -80C (or in liquid nitrogen, for PBMCs) for each sample. Samples will be transported every 3-6 months from MGH and BIDMC to BWH, which will serve as the central biorepository for the study. The location of each sample will be catalogued using Freezerworks, a sophisticated biorepository management and inventory program.

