6.5 Statistical analysis for secondary endpoints

Hypothesis 2: DFO will attenuate peak postoperative increases in urinary markers of tubular injury (NGAL and KIM-1) and iron and oxidative stress, and will reduce the incidence of myocardial injury, atrial fibrillation, prolonged mechanical ventilation, and sepsis. For binary variables we will use the χ^2 test to compare the proportion of patients in each group who develop the endpoint. For continuous variables we will compare baseline (preoperative)-adjusted peak postoperative levels of each marker in DFO- versus placebo-treated patients using the two sample t-test or Wilcoxon rank-sum test depending on the distribution. We will also use a Generalized Estimating Equation for repeated measures to analyze longitudinal assessments of each marker in DFO- versus placebo-treated patients. For analyses of urinary tubular injury markers, we will perform sensitivity analyses using a global rank endpoint to account for anuria as a competing risk.^{101, 102} Finally, we will evaluate a composite endpoint of any renal or extrarenal acute organ injury or hospital mortality.

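### Does section 6.5 need to spell out the GEE time terms and which samples count towards the peak marker level?

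*Combined protocol and SAP*

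**What the plan says.** Under Hypothesis 2, section 6.5 gives two analyses for continuous markers. The first compares baseline-adjusted "peak postoperative levels of each marker" by t-test or Wilcoxon test. The second is introduced as an addition: "We will also use a Generalized Estimating Equation for repeated measures to analyze longitudinal assessments of each marker in DFO- versus placebo-treated patients". Section 6.5 gives no time coding, interaction term or tested contrast, and no list of samples for the peak.

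Sampling times are given elsewhere. Section 5.4 sets five for blood and urine: preoperative, end of bypass (CPB), ICU arrival, and postoperative days (POD) 1 and 2. The Synopsis gives the same schedule for NGAL and KIM-1: "assessed preoperatively, at the end of CPB, on arrival to the ICU, and daily for 2 days postoperatively". For the iron and oxidative-stress markers, section 6.4 says only that they are measured before and after surgery and points to Figure 4, which is not reproduced in the text available here.

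**The concern.** Two things look open. First, end of CPB might or might not count as postoperative. Section 1.2.2 separates the intraoperative period from the postoperative one in the investigators' earlier cohort ("We measured plasma catalytic iron pre-, intra-, and postoperatively in 250 adults undergoing cardiac surgery with CPB"), and the Synopsis schedule attaches the word only to the two daily samples. The sample in doubt is the one that matters most for catalytic iron, since section 1.2.2 reports: "Catalytic iron levels peaked at the end of CPB".

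Second, the infusion lasts 12 hours and starts about an hour before surgery. End of CPB and ICU arrival normally fall inside it, and POD1 and POD2 normally after it. A GEE with one averaged treatment coefficient would dilute an effect present only during the infusion. The later period matters too, because section 1.2.2 ties AKI and RRT/death to catalytic iron in the "highest versus lowest quartile on postoperative day 1". If both choices were left until after unblinding, the answer to Aim 2 could depend on them.

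**Working it through.** **The plan's own figure.** The only stated power calculation is for AKI (section 6.3): 50% v 34%, two-sided 0.05, 80% power, 148 per arm. With pooled variance and no continuity correction, n per arm = [1.96·√(2·0.42·0.58) + 0.842·√(0.50·0.50 + 0.34·0.66)]² / 0.16² = (1.368 + 0.580)² / 0.0256 ≈ 148.2. Rounded up this is 149 per arm, 298 in total, against 296 stated. Power at 148 per arm is 79.9%. The figure reproduces, and nothing about the markers enters it.

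**Which samples form the peak.**

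1. The Synopsis uses one sentence for iron status, oxidative stress and monocyte phenotype, and says each is assessed before and after surgery.
2. For monocytes, section 5.4 says: "At two time points (preoperatively and at the end of CPB) we will also isolate PBMCs and store them in liquid nitrogen". The same section uses them to study the "inflammatory phenotype of monocytes postoperatively". The only post-baseline monocyte sample is end of CPB, so the plan's term includes it. The Synopsis sentence applies that term to catalytic iron as well.
3. Section 6.1 also uses the term broadly: urine output for postoperative AKI is monitored from the start of surgery.
4. Where a narrower window is meant, the plan states it: Table 5 limits peak troponin I to POD1 and POD2.
5. Section 5.4 lists the iron assays in its paragraph on the 10 mL draws (ICU arrival, POD1, POD2). That cannot restrict them to those draws, because section 6.5 needs a preoperative baseline, which is a 25 mL draw, as is end of CPB. The volumes agree with five draws: 2 × 25 + 3 × 10 = 80 mL.

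Four post-baseline samples is the natural reading.

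**What a single GEE coefficient would cost.** Let c be the share of the effect that persists to POD1 and POD2. The share retained is (2 + 2c)/4: 0.50 at c = 0, 0.75 at c = 0.5 and 1.0 at c = 1.

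For power, assume 150 per arm (300 analysable, section 6.6), unit SD, equal correlation r = 0.5 and baseline adjustment. None of the SD, the correlation or the effect comes from the documents. The SD of a mean of k samples is √((1 + (k−1)r)/k − r²), which is 0.707 for k = 2 and 0.612 for k = 4. Power = Φ(Δ/(SD·√(2/150)) − 1.96), with √(2/150) = 0.1155.

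| Assumed effect during infusion | Estimate | Δ | Power |
|---|---|---|---|
| 0.25 SD | during-infusion mean | 0.25 | 86.5% |
| 0.25 SD, c = 0 | four-sample average | 0.125 | 42.4% |
| 0.25 SD, c = 0.5 | four-sample average | 0.1875 | 75.5% |
| 0.25 SD, c = 1 | four-sample average | 0.25 | 94.2% |
| 0.50 SD, c = 0 | four-sample average | 0.25 | 94.2% |

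**What the sample list would cost.** A separate simulation (150 per arm, 3,000 replicates) assumed placebo means of 1.0, 0.6, 0.2 and 0 SD at the four later samples and correlations of 0.3 and 0.6.

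- Effects of 0.4 and 0.3 SD in the first two samples only: peak-test power is 76–77% with all four samples, 29% without end of CPB and 4–5% with POD1–2 alone.
- A constant effect of 0.3 SD: 79–87% whichever samples are used.

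So the list matters only if the effect is early and end of CPB is dropped, which is the reading the text disfavours.

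**The case for a change.** The best case for acting is that it would be nearly free. Section 6.5 is the only place where these analyses are specified, and it is silent on both points. The plan's wording for postoperative is not uniform, and its one explicit peak window (troponin) is narrower than four samples. An early effect is plausible: Table 2 gives deferoxamine an elimination half-life of 0.28 hours, and section 1.4 chose a 12-hour infusion because catalytic iron is highest around surgery. Two sentences before unblinding would remove any later choice.

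The silence is real, and recording the model terms before unblinding would do no harm. The rest carries less weight. The half-life describes the drug and does not show that marker effects end with the infusion. The Synopsis schedule belongs to NGAL and KIM-1, where the word simply dates the two daily samples. Section 1.2.2 describes an earlier cohort. The dilution needs both a main-effect-only GEE and little persistence, and the documents state neither. Prescribing separate during- and post-infusion estimates is one preference among several. For the seven iron and oxidative-stress markers in section 6.4 it would yield 7 × 2 = 14 estimates, and it would still leave the working correlation and baseline handling unstated.

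**Conclusion.** This is ordinary missing detail that a competent analyst fills sensibly. No stated rule, figure or definition is shown to be wrong. The peak is best read as the maximum over end of CPB, ICU arrival, POD1 and POD2. A repeated-measures GEE on a fixed schedule would ordinarily carry categorical time and a treatment-by-time term, which shows both periods without averaging one into the other.

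The size is nil for the primary endpoint, the sample size and the stated power. For the markers, the retained share runs from 0.50 to 1.0, and only under a single averaged coefficient. Every power figure above rests on assumed effects, SDs, correlations and profiles. At an effect of about 0.5 SD, or with most of the effect persisting, the difference becomes small. The iron and oxidative-stress markers are exploratory in the Synopsis, although section 6.4 lists them with the secondary endpoints, and the GEE supplements the peak comparison. The conclusion on the peak rests on the text alone, since Figure 4 could not be seen.

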6.6 Modified intention-to-treat analysis

The final analysis will be limited to patients who are initiated on the study drug, irrespective of whether they are able to complete the entire 12h infusion, consistent with a modified intention-to-treat analysis. Patients who consent but are subsequently found to be ineligible prior to initiation of the study drug infusion (e.g., if a patient develops a new fever several hours prior to surgery) will be withdrawn. In such cases, the reason for the withdrawal will be documented and reported, but these patients will not be included in the final analysis, nor will they count toward the total enrollment target of 300 analyzable patients. Accordingly, we anticipate enrolling up to 330 patients (10% buffer) to obtain 300 analyzable patients, accounting for withdrawal prior to receipt of study drug.

7. RISKS AND DISCOMFORTS

Overview of DFO safety profile

DFO was the first iron chelator approved by the FDA (in 1968), and thus has a long track record of safety. DFO is generally very well tolerated, as patients with genetic hemoglobin disorders complicated by iron overload often receive DFO on a daily basis for their entire lives.¹⁰³ Rare but serious potential adverse effects of DFO include hypersensitivity reactions, hypotension, acute respiratory distress syndrome (ARDS), infection, vision changes, and hearing loss.

7.1 Hypersensitivity reactions

Hypersensitivity reactions, including anaphylaxis, have very rarely been reported with DFO (less than 1 in 10,000). In a phase 2 RCT of DFO at 32 mg/kg per day for 3 days in patients with ICH, none of the 147 DFO-treated patients experienced anaphylaxis.⁸²

7.2 Hypotension

DFO may cause hypotension if infused very rapidly (>15 mg/kg/h). For example, DFO-induced hypotension was initially observed in two of three children with acute iron poisoning who received large doses of IV DFO (ranging from 800-1500mg) administered over 15 minutes.¹⁰⁴ Accordingly, the FDA-recommended infusion rate for IV DFO for acute iron intoxication is to not exceed 15 mg/kg/h. Thus, the DFO dosing regimen in the current study (30 mg/kg over 12h hours, which equates to 2.5 mg/kg/h) is 6-fold lower than the maximum FDA-recommended infusion rate.

Regarding dose, the maximum FDA-approved dose for DFO for acute iron intoxication is 6g/day, or ~86 mg/kg in a 70-kg adult, and doses as high as 150 mg/kg/day for 3 months have been used without toxicity.¹⁰⁵ Thus, the dosing of 30 mg/kg in the current study is far below the maximum FDA-approved dose, and is unlikely to cause hypotension. Supporting this, one study administered DFO as an IV bolus of 500mg over 10 minutes in patients with STEMI.⁸¹ This infusion rate of 50mg/min, despite being more than 15-times higher than the infusion rate in the current study (30 mg/kg over 12h, or ~3 mg/min in a 70-kg individual), did not result in any hypotension. Importantly, hypotension was also not observed in the studies of IV DFO for acute organ injury prevention in humans, summarized in **Table 3**. The largest such study, a phase 2 RCT of DFO at 32 mg/kg per day for 3 days in patients with ICH, found the incidence of hypotension was similar in the DFO-treated patients (1 of 144 [1%]) compared to placebo-treated patients (2 of 147 [1%]).⁸²

7.3 ARDS

DFO may rarely cause ARDS when administered in very high doses. Tenenbein et al. described four adult patients with acute iron overdose who developed ARDS after receiving high doses of IV DFO (15 mg/kg/h) for prolonged periods of time.¹⁰⁶ DFO doses received by the four patients ranged from 24 to 120g delivered over 32 to 72 hours, corresponding with doses 10 to 50-times higher than those that will be used in the current study. The High-Dose Deferoxamine in Intracerebral Hemorrhage (HI-DEF) study (clinicaltrials.gov NCT01662895), which investigated a continuous IV infusion of DFO at 62 mg/kg/day for 5 consecutive days versus normal saline placebo in patients with ICH, was stopped early due to the observation of 6 cases of ARDS among the DFO-treated patients after enrollment of 42 subjects. Three modifications to the DFO dosing regimen were subsequently implemented: 1) the 62 mg/kg/day dose was reduced to 32 mg/kg/day; 2) the 5-day infusion was reduced to 3 days; and 3) the continuous infusion was changed to daily interrupted infusions of 12h/day, based on data that DFO-associated ARDS is more likely to occur in patients treated for longer than 24h.¹⁰⁶ These changes to the DFO dosing regimen were implemented in a phase 2 RCT of DFO in patients with ICH, and the incidence of ARDS was similar in the DFO- (2 of 144 [1%]) compared to placebo-treated patients (1 of 147 [1%]).⁸²

7.4 Infection

In patients with chronic iron overload it has been reported that infections, especially gastroenteritis with *Yersinia* species, may be promoted by DFO. Among dialysis patients receiving DFO, rare cases of mucormycosis have also been reported. An increased risk of infection has not been reported with short-term use of DFO for acute organ injury prevention (**Table 3**). The largest such study, a phase 2 RCT of DFO at 32 mg/kg per day for 3 days in patients with ICH, found the incidence of infection was similar in DFO- and placebo-treated patients (35 of 144 [25.0%] and 36 of 147 [24.5%], respectively).⁸²

7.5 Vision changes

DFO administered in high doses and over long periods of time has rarely been linked to vision changes. Effects on the eye were first noted when very high doses (>100 mg/kg/day) were given.¹⁰⁷ Symptoms may include night-blindness, impaired color vision, impaired visual fields, and reduced visual acuity. Severe cases may show signs of retinitis pigmentosa on fundoscopy, whereas milder cases are only demonstrable with electroretinography. The main risk factor appears to be high doses of DFO.¹⁰⁸

The prevalence of DFO-associated ocular toxicity was evaluated in 84 children who were receiving DFO for an average of 6.6 years for transfusion-related iron overload due to thalassemia.¹⁰⁹ The DFO dosage was 25-50 mg/kg/day. Ophthalmic screening was performed at baseline and on an annual basis. Only one patient had abnormal findings, with central blurring, retinal pigmentary changes, and a reduced central response on electroretinography. This patient had a 3-year history of poor adherence and was temporarily receiving IV DFO at 50 mg/kg/day; all symptoms promptly recovered after changing to subcutaneous administration. Notably, vision changes have not been described in any of the short-term studies of DFO use for acute organ injury prevention (**Table 3**). The largest such study, a phase 2 RCT of DFO at 32 mg/kg per day for 3 days in patients with ICH, found that none of the 147 DFO-treated patients experienced vision changes.⁸²

